5.0 Research Plan

5.1 Investigate whether the ultrasound imaging can enhance soft tissue tumor localization.

(a) Following the standard clinical procedure, daily KV-CBCT image for each patient will be acquired and used to guide for patient setup prior to treatment delivery. Because of limited soft tissue contrast in KV-CBCT to observe the soft tissue organ, such as the prostate, the added ultrasound image may enhance soft tissue localization prior to treatment for these patients.

The ultrasound device will be calibrated to the treatment iso-center via an external camera system and infrared markers on the ultrasound (US) probe. A commercially available passive arm will be acquired and attached to the ultrasound probe. Following our current clinical protocol, the patient treatment position will be determined solely based the daily KV-CBCT. After KV-CBCT guidance, a pre-treatment US image will be acquired for the study but not used for patient positioning. The success of this specific aim is defined as that the tumors can be visualized in the ultrasound images in at least 80% of patients enrolled.

(b) Investigate whether the presence of a passive arm will interfere with radiation delivery during each treatment.

In order to monitor tumor or organ motion during radiation, the US probe will be placed using a passive arm, as shown in the figure below. This passive arm will be attached to the treatment couch and also in contact with the patient during the radiation. Although the passive arm is commercially available, we plan to test whether the presence of the US probe will interfere radiation delivery during each treatment. Specifically, we will test: (a) whether the passive arm reduces the clearance between the patient and the gantry of the linear accelerator; (b) whether the passive arm can hold a consistent contact pressure with the patient under normal breathing motion; (c) whether the passive arm can be automatically released if a patient makes a large movement. The success of this specific aim is defined as that at least 80% of patients are able have the ultrasound probe attached during the entire treatment course.

Figure 1.

(c) Investigate whether the presence of the ultrasound probe will interfere with the choice of radiation beams and degrade plan quality

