The presence of the US probe and the passive arm may block the access of some radiation beams. The specific aim of this study to investigate whether altering the radiation beam directions will affect the treatment plan quality. Our preliminary planning data[1] showed that it is necessary to choose different radiation beam angles, but the impact on treatment plan quality is not clinically significant for most patients. Patients for whom treatment plan quality is in the opinion of the treating physician adversely impacted by alteration of beam angles required by presence of the US probe will be treated with the non-altered plan, and thus be included in step 5.1(a), but excluded from 5.1(b&c), as US probe will be removed prior to treatment in these cases to allow for treatment with the best possible plan. We expect this to be rare. The success of this specific aim is defined as that the quality of the plans for 80% of patients will not be affected in the presence of the

ultrasound probe, defined as no more than a 2% decrease in tumor coverage, and also no more than a 2% increase in the dose to the most critical normal tissue for that tumor location (Prostate: dose to hottest 10 cc of rectum.)

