7.0 Statistical Considerations

Because of limited funding from NIH, the number of patients that are planned to be enrolled into this protocol will be small and potentially lacking of the statistical power. The primary purpose of this study is a feasibility study to test whether a combined CBCT and ultrasound image guidance is clinically feasible. Our analysis is primarily descriptive and does not require any advanced statistics to analyze the endpoints. As a measure of protocol success we expect that:

- 1) Over 80% of patients have ultrasound images which are clinically adequate for treatment set-up in the judgment of the treating physician.
- 2) Over 80% of patients are able to undergo ultrasound based tumor tracking during treatment.
- 3) The quality of treatment plans for more than 80% of patients will not be affected.
- 4) No adverse events related to the ultrasound probe are noted during treatment.

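### Aim 5.1(c) drops patients whose probe-altered plan the physician rejects, so its 80% plan-quality rate uses a denominator selected on the outcome

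*Combined protocol and SAP*

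**What the plan says.** Section 5.0, under 5.1(c), gives the purpose of the aim as "to investigate whether altering the radiation beam directions will affect the treatment plan quality". The success criterion is "The success of this specific aim is defined as that the quality of the plans for 80% of patients will not be affected", with unaffected "defined as no more than a 2% decrease in tumor coverage, and also no more than a 2% increase in the dose"; this second limit concerns the organ most at risk, taken for prostate as the hottest 10 cc of rectum.

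Between the purpose and the criterion comes the exclusion. "Patients for whom treatment plan quality is in the opinion of the treating physician adversely impacted by alteration of beam angles" required by the probe are treated with the non-altered plan, "and thus be included in step 5.1(a), but excluded from 5.1(b&c"). The reason given is that the probe is removed before treatment in these cases. On frequency the protocol says only "We expect this to be rare".

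Three other places bear on the denominator:

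- Aim 5.1(a) is scored on everyone: "the tumors can be visualized in the ultrasound images in at least 80% of patients enrolled".
- Section 7.0, item 3, reads "The quality of treatment plans for more than 80% of patients will not be affected". It does not say whether the exclusion carries over.
- Section 8.2 records how many patients had the probe attached and how many had it removed. It does not ask for the 2% result in those whose plan was rejected.

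**The concern.** The patients removed from 5.1(c) are those in whom a clinician has already concluded that the probe harmed the plan. An estimate of how often the probe leaves the plan unharmed should not be made after setting them aside.

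The stated reason does not cover this aim. Removing the probe affects delivery. Aim 5.1(c) compares two plans, and that comparison can be made at the planning stage whether or not the probe is later used. For the physician to judge the altered plan and fall back on the non-altered one, both should already exist.

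At stake is whether the plan-quality criterion can be reported as met when it is not met among all patients planned. Section 8.8 says the feasibility data will be used to design a later, adequately powered treatment protocol. An optimistic rate here would understate how often the probe cannot be used without cost to the plan.

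**Working it through.** **Inputs.** N = 30 (Section 3.0). The 5.1(c) threshold is 80%, read as at least 80%; Section 7 item 3 requires more than 80%. The protocol states no power or rejection figure, so there is nothing to reproduce. Two counts are assumptions: r, the plans rejected by the physician, and f, the plans outside 2% among the patients who are kept.

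**Formulas.**

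- As written: (30 − r − f)/(30 − r)
- All patients, rejected plans outside 2%: (30 − r − f)/30
- All patients, rejected plans within 2%: (30 − f)/30

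**Example, r = 3 and f = 5.**

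- As written: 22/27 = 81.5%, success
- All 30, rejected plans outside 2%: 22/30 = 73.3%, failure
- All 30, rejected plans within 2%: 25/30 = 83.3%, success

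**Range, f = 0 to 6 and r = 1 to 4 (28 combinations).**

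- *Every rejected plan outside 2%.* The 5.1(c) verdict changes from success to failure in 6 of 28: f = 3 with r = 4; f = 4 with r = 3 or 4; f = 5 with r = 2, 3 or 4. Under the more-than-80% wording of Section 7 it changes in 10 of 28, if the exclusion applies there.
- *Every rejected plan within 2%.* The 5.1(c) verdict changes the other way in the four combinations with f = 6. With r = 1, for example, 23/29 = 79.3% as written becomes 24/30 = 80.0%.
- *Rejections rare (r = 1 or 2), every rejected plan outside 2%.* The 5.1(c) verdict changes in 1 of 14 combinations (f = 5, r = 2: 23/28 = 82.1% against 23/30 = 76.7%).

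**Chance of meeting the 5.1(c) threshold.** Let p be the true proportion of plans within 2%, and q the share of outside-2% plans that the physician rejects. Each of 30 patients is within 2% (probability p), outside and rejected ((1 − p)q), or outside and kept ((1 − p)(1 − q)). Success probabilities are exact multinomial sums. No within-2% plan is rejected in this model, so it can show only upward bias. Expected rejections are 30(1 − p)q.

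| p | q | Expected rejections | With exclusion | All 30 |
|---|---|---|---|---|
| 75% | 0.5 | 3.75 | 81.7% | 34.8% |
| 75% | 0.25 | 1.88 | 52.1% | 34.8% |
| 80% | 0.5 | 3.0 | 92.4% | 60.7% |
| 80% | 0.25 | 1.5 | 74.2% | 60.7% |
| 80% | 0.1 | 0.6 | 63.5% | 60.7% |
| 90% | 0.5 | 1.5 | 99.7% | 97.4% |
| 90% | 0.1 | 0.3 | 97.7% | 97.4% |

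The exclusion matters when the true rate is near or below 80% and a sizeable share of affected plans is rejected. It hardly matters at 90%.

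**The case against.** **The direction of bias is not guaranteed.** The trigger is a physician's opinion, while the outcome is a numerical rule on tumor coverage and one rectal dose. A physician might reject a plan because of bladder, urethra or femoral-head dose, all listed in Section 6.0, while the plan stays within 2%. This stands. A reader might infer that the exclusion necessarily inflates the result; the documents do not support that, because nothing ties the veto to the 2% rule.

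**The large contrasts need scenarios that the protocol does not expect.** It calls rejection rare and describes the impact on plan quality as not clinically significant for most patients. This stands as a limit on size. The expectation has no number behind it, however, and the planning study cited for the small impact is, by its title, about liver tumors, whereas this trial enrolls prostate patients.

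**The study is descriptive.** Section 7.0 makes no test or power claim, so no formal error rate is at risk. That lowers the severity. It does not remove the point, because the protocol still declares success against a fixed percentage, and a descriptive proportion also needs the right denominator.

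**Section 7 item 3 can be read as covering all patients, and Section 8.2 counts probe removals.** Both are fair. But item 3 does not override the explicit exclusion in Section 5, and a count of removals shows neither why the probe came off nor whether the plan met the 2% rule.

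**That both plans exist is an inference.** The protocol does not say that a complete altered plan is produced before every veto. It is the natural reading of a judgement about plan quality, but it should be made explicit.

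A reader might also infer that the exclusion is sound for 5.1(b), since the probe is not used. The text does not support that either. Section 5.1(b) succeeds if at least 80% of patients can keep the probe attached for the whole course, and a vetoed patient could not.

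**Conclusion.** The point holds. By explicit rule, the 5.1(c) success rate omits patients selected by a judgement about the outcome it measures, and no other text puts them back. The bias is towards success to the extent that rejected plans are outside 2%. In the assumed example it turns 73.3% into 81.5% and changes the verdict. It is small if rejections are rare: about 3 percentage points in the chance of success at a true rate of 80% with a tenth of affected plans rejected. It reverses if the rejected plans are within 2%. All these sizes rest on assumed rejection counts or shares.

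This should be corrected before the rate is reported, but it does not undermine the study. The physician's veto is clinically right and is not in question. The documents do not show that 5.1(c) will be falsely declared a success, only that the rule as written allows it.

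**What to change.** 1. Keep the physician's veto and treatment with the non-altered plan.
2. Delete the exclusion from 5.1(c). State that the altered and non-altered plans are both completed, and the 2% result recorded, for every patient planned, including those whose altered plan is rejected.
3. Score 5.1(c) and Section 7 item 3 on all patients planned, with the 2% definition unchanged.
4. Report a 2×2 table of 2% result (within or outside) by altered plan delivered or rejected. Beside it, give the rate with every rejected plan counted as affected, so that a plan the physician would not deliver is not hidden by passing the 2% rule.
5. Report 5.1(b) also with vetoed patients counted as not attached for the course.

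The cost is a change of wording in Section 5.1 and Section 7 item 3, and one extra recorded result per rejected plan. No new planning is needed if, as the veto implies, both plans already exist. Patient care does not change. The downside is that the success rates may be less favourable: certainly no better for 5.1(b) with vetoed patients counted as not attached, and for 5.1(c) depending on whether rejected plans meet the 2% rule.

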6.0 Study Parameters

The study parameters collected are the US images acquired prior to each treatment and during radiation delivery. Pre-treatment KV-CBCT images will also be collected for dosimetric analysis. Specifically, the tumor location detected from combined US/KV-CBCT images will be compared with using KV-CBCT alone. Using the KV-CBCT the gold standard, 3D radiation dose distributions will be re-calculated according to the tumor localizations using KV-CBCT alone and using combined US/KV-CBCT. For SBRT prostate cancer, we will compare the following dosimetric endpoints, extracted from dose volume histograms.

Organ Name	Endpoint 1	Constraints
PTV_HD*	V5000 cGy	> 50%
PTV_LD*	V3625 cGy	> 95%
PROSTATE	V3625 cGy	> 95%
BLADDER	D0.03 cc	< 5250 cGy
RECTUM_ANT	D0.03 cc	<5000 cGy
RECTUM_LAT	D3cc	< 4000 cGy
RECTUM_POST	V0.03 cc	< 2250 cGy
URETHRA	V0.03cc	< 5000 cGy
URETHRA	D1cc	< 4500 cGy

PTV_HD = planning target volume in high dose prescription dose of 5000 cGy

PTV_LD = planning target volume in low prescription dose of 3625 c Gy.

For patients treated with conventional multiple fractionation, we will compared the following dosimetric endpoints, extracted from dose volume histograms.

Organ Name	Endpoint 1	Constraints	Planned	comments
CTV_7800	V7800 cGy	> 99%		
PTV_7800	V7800 cGy	> 95%		
BLADDER	V7000 cGy	< 10%		
BLADDER	V6000 cGy	< 20%		
RECTUM	V7000 cGy	< 10%		
RECTUM	D10cc	< 7000 cGy		
RECTUM	V5000 cGy	< 30%		Without pelvic nodes
RECTUM	V5000 cGy	< 50%		With pelvic nodes
FEMORAL HEAD_L	V5000 cGy	< 5%		
FEMORAL HEAD_R	V5000 cGy	< 5%		
PENILE BULB	Dmean	< 5250 cGy		

For patients with prostatectomy receiving post-operative radiotherapy with conventional multiple fractionation, we will compared the following dosimetric endpoints, extracted from dose volume histograms.

Organ Name	Endpoint 1	Constraints	Planned	comments
CTV_7000	V7000 cGy	> 99%		
PTV_7000	V7000 cGy	> 95%		
BLADDER	V6500 cGy	< 40%		
BLADDER	V4000 cGy	< 60%		
RECTUM	V6300 cGy	< 10 %		
RECTUM	D10 cc	<6300 cGy		

RECTUM	V4500 cGy	< 30 %		Without Pelvic nodes
RECTUM	V4500 cGy	< 50%		With pelvic nodes
FEMORAL HEAD_L	V5000 cGy	< 5%		
FEMORAL HEAD_R	V5000 cGy	< 5%		
PENILE BULB	Dmean cGy	< 5250 cGy		

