1.0 Background and Rationale

Hypofractionated radiotherapy, the delivery of higher dose per fraction with reduced number of treatment fractions, is a promising treatment option for many disease sites. Hypofractionated radiotherapy inherently requires a smaller patient setup margin which in turn necessitates the use of image guidance to alleviate the increased risk of geometric misses and deleterious clinical outcomes.

The main thrust of modern image guidance is to localize the soft tissue target and represents a major paradigm shift from the verification of bony landmarks. The predominant form of image guidance is on-board kilo-voltage cone beam CT (KV-CBCT). Although KV-CBCT is highly effective in improving accuracy of the patient setup prior to treatment, CBCT has two major deficiencies when applied to verify hypofractionated radiotherapy or radiosurgery.

First, KV-CBCT only provides a “snapshot” of patient anatomy at the time of imaging, but not during actual radiation delivery. Secondly, flat panel based KV-CBCT employed in radiation therapy is less than effective in discriminating a soft tissue target in a low contrast environment. Localization of abdominal lesions for hypofractionated treatment is challenging with KV-CBCT. Alternative imaging methods are needed. Ultrasound imaging is one of the important technologies that are capable of soft tissue localization in the abdomen. We have a commercially available ultrasound system in our department. This system has been predominantly used for prostate patients, localizing the prostate prior to treatment. Ultrasound imaging alone, however, suffers insufficient of field of view to visualize a proper patient position for radiotherapy.

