2.0 Objectives

Purpose of this protocol is to investigate the feasibility of combining on-board CBCT with ultrasound imaging to overcome the shortcomings of CBCT or ultrasound imaging alone for imaging guided radiotherapy delivery. Specifically, we will investigate (a) whether the ultrasound imaging can enhance soft tissue tumor localization; (b) whether the presence of a passive arm is interfering radiation delivery during each treatment; (c) whether the presence of the ultrasound probe will affect the choice of radiation beams and degrade treatment plan quality.

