8.8 Importance of the knowledge to be gained

The research aims to develop a novel non-invasive approach of image guidance of hypofractionated SBRT of patients with abdominal and pelvic tumors with the capability of continuous monitoring during radiation delivery. Successful monitoring of target position during treatment is expected to reduce margins required during radiation treatment, and thereby reduce dose to surrounding normal tissue. This has been demonstrated clinically using real-time tracking technology using implanted markers in prostate cancer, but in this study would be able to be done non-invasively using ultrasound.

The analysis of the recalculated dosimetry will show the uncertainty of dose delivery using current CBCT and ultrasound image guidance methods and shed light on the degree of improvement that can be achieved when they are combined. The data from the feasibility studies will be immensely useful for designing a treatment protocol with adequate statistical power to prove the improvement in treatment accuracy and efficacy. In turn, a cost-benefit analysis can then be made in terms of resource allocation, treatment efficiency and margin reduction. The information will be most significant as a baseline for assessing the cost-effectiveness of the next generation of advanced IGRT machines such as those employing on-board MRI.

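### Section 6.0 uses KV-CBCT as the gold standard in a comparison where KV-CBCT is one of the two methods, so the secondary localization and dose analysis cannot support the improvement statement in Section 8.8

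*Combined protocol and SAP*

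**What the plan says.** Section 6.0 plans two linked comparisons. For position, "the tumor location detected from combined US/KV-CBCT images will be compared with using KV-CBCT alone". For dose, "Using the KV-CBCT the gold standard, 3D radiation dose distributions will be re-calculated according to the tumor localizations using KV-CBCT alone" and also with the combined method; dose-volume endpoints are then compared for SBRT, conventional and post-operative patients. No other reference for target position appears anywhere in the document.

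Three other places bear on this choice:

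- Section 1.0 says that "flat panel based KV-CBCT employed in radiation therapy is less than effective in discriminating a soft tissue target in a low contrast environment". Section 5.0 applies the same point to this trial's target: "Because of limited soft tissue contrast in KV-CBCT to observe the soft tissue organ, such as the prostate, the added ultrasound image may enhance" localization.
- Section 2.0, objective (a), asks "whether the ultrasound imaging can enhance soft tissue tumor localization".
- Section 8.8 says the recalculated dosimetry will "shed light on the degree of improvement that can be achieved when they are combined".

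Ultrasound does not influence setup in the trial. Under Section 5.0, "the patient treatment position will be determined solely based the daily KV-CBCT".

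**The concern.** A gold standard is the measurement taken as true. Here that role goes to one of the two methods under comparison, and to the one whose weakness is the reason for the study. If the sentence is followed as written, KV-CBCT agrees perfectly with itself and any shift seen with ultrasound looks like an error of the combined method, even where the shift corrects a KV-CBCT miss.

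What is at stake is the secondary localization and dosimetric analysis. It is the only planned analysis that could put a size on the gain mentioned in objective (a) and Section 8.8, and Section 8.8 expects the study's data to inform the design of a later, powered protocol. A comparison biased towards KV-CBCT would be a poor basis for that.

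**Working it through.** The plan gives no effect size, SD or margin for this comparison, so there is no figure to reproduce. The check is mainly logical. All mm values and the dose profile below are illustrative assumptions.

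**1. Localization, as written.** For one fraction let T be the true target position, C the KV-CBCT localization and U the combined localization. With KV-CBCT as reference:

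- error of KV-CBCT = |C − C| = 0, always
- error of combined = |U − C| ≥ 0

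Suppose C = T + d and U = T, so ultrasound corrects the miss fully. Against the truth the errors are d for KV-CBCT and 0 for combined. Against the KV-CBCT reference they are 0 and d. The ranking is reversed, and the number of patients does not enter.

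**2. Illustration.** 400,000 draws in three dimensions, with independent normal errors on each axis. Entries are mean 3D errors in mm and the share of draws in which the combined method is closer to the reference.

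| SD per axis, KV-CBCT / combined | True position as reference: KV-CBCT, combined, share | KV-CBCT as reference: KV-CBCT, combined, share |
|---|---|---|
| 3 / 0 | 4.8, 0.0, 100% | 0, 4.8, 0% |
| 3 / 1 | 4.8, 1.6, 95% | 0, 5.0, 0% |
| 3 / 2 | 4.8, 3.2, 74% | 0, 5.8, 0% |
| 3 / 3 | 4.8, 4.8, 50% | 0, 6.8, 0% |
| 2 / 3 | 3.2, 4.8, 26% | 0, 5.8, 0% |

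The 0% column follows from the identity in step 1; the simulation does not confirm it independently. The rows add two things. A perfect combined method (3 / 0) is charged 4.8 mm that belongs entirely to KV-CBCT. Rows 3 / 2 and 2 / 3 show the same mean disagreement, because the variance of U − C on each axis is 3² + 2² = 2² + 3² = 13, yet the combined method is the better one in the first and the worse one in the second. The size of the disagreement alone cannot tell these apart.

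**3. Dose.** A one-dimensional toy model: target half-width 20 mm, dose plateau half-width 25 mm with sigmoid fall-off (scale 3 mm), coverage counted at 80% of prescription or more, rectum 22 to 40 mm posterior. The plan is displaced from the reference anatomy by U − C.

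| Displacement | Change in target coverage (percentage points) | Change in mean rectal dose (fraction of prescription) |
|---|---|---|
| 2 mm anterior / posterior | −3 / −3 | −0.07 / +0.09 |
| 4 mm anterior / posterior | −8 / −8 | −0.13 / +0.18 |
| 6 mm anterior / posterior | −13 / −13 | −0.17 / +0.28 |

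Coverage falls in either direction because the plan is centred on the reference. Rectal dose falls or rises with the direction of the shift. A fall means only that the dose moved away from the rectum; it does not show that the target was located better.

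**4. Which conclusions use this comparison.** The success rules in Section 5.0 and the four expectations in Section 7.0 concern visualization or image adequacy, probe attachment or tracking, plan quality, and probe-related adverse events. None uses the Section 6.0 comparison of localizations.

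**The case against.** The gold-standard sentence is loosely written. Section 6.0 has just said that KV-CBCT images are collected for dosimetric analysis, so the clause may mean only that dose is computed on KV-CBCT anatomy, once under each localization. Section 6.0 also defines no error score; it says the locations are compared. The distance formula above is one literal way to carry that out, not a stated endpoint. Finally, this is a descriptive feasibility study, and Section 8.8 leaves proof of improvement to a later protocol.

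Much of this stands. The benign reading is possible, and under it nothing need be scored as an error. It does not rescue Section 8.8, though: with no independent position reference, the two localizations can be shown to differ, but not which is nearer the target (rows 3 / 2 and 2 / 3 above). A descriptive result with the wrong reference can still mislead.

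Two stronger readings are tempting and should be resisted. A reader might infer that the combined method can only tie or lose on every endpoint. That holds for distance from the reference and, with the plan centred there, for target coverage; it fails for single normal-organ endpoints, which move both ways. A reader might also infer that the trial as a whole cannot meet its aim. The documents do not support that: the stated purpose is feasibility, and aim (a) has its own success rule, visualization in at least 80% of patients.

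**Conclusion.** The point holds for the secondary localization and dosimetric analysis. Taken literally, Section 6.0 gives KV-CBCT zero localization error by construction and charges a correct ultrasound correction of d mm to the combined method in full. Taken loosely, it still names no independent truth. On either reading the analysis cannot support the degree-of-improvement statement in Section 8.8, and a larger sample would not change this.

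The literal conclusion assumes that error is measured as distance from the named reference and, for coverage, that the plan is centred on it. The simulation also assumes independent errors; correlated errors would shrink the distances but leave the zero for KV-CBCT in place.

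The feasibility conclusions stand, and no treatment position depends on this comparison. The text should be corrected before analysis, but the defect does not threaten the main purpose of the study.

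**What to change.** 1. In Section 6.0, delete the clause that makes KV-CBCT the gold standard. State that the two localizations are paired measurements and that neither is the reference.
2. For each axis, report D = U − C by patient and fraction: the mean, the between-patient SD (s_b), the within-patient SD over fractions (s_w), and 95% limits of agreement, mean ± 1.96 × √(s_b² + s_w²), so that repeated fractions are allowed for.
3. Report paired differences in the listed dose-volume endpoints twice, once with the KV-CBCT position taken as true and once with the combined position taken as true. State whether normal-organ contours stay as seen on KV-CBCT or move with the target.
4. In Section 8.8, replace the improvement wording with the size of the disagreement between the two localizations and its impact on dose.

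This will not show that ultrasound improves accuracy. It removes a comparison biased towards KV-CBCT and a claim the data cannot carry. If the improvement claim is to be kept, an independent reference for target position has to be named instead.

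The cost is a change of wording, a second recalculation pass on images already collected, and a more modest claim. No extra patients or procedures are needed.
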